Appendix 14: Checklist for adherence counselling (HIV and TB)

Pre HIV test counselling check list: individual or in group

Reasons and benefits of having an HIV test

What the patient knows about HIV?

What is HIV and its modes of transmission

A brief description of prevention options

Reinforce that results will remain confidential

Reinforce the fact that the patient can deny the test, but explain the importance of doing it

The HIV testing process (finger-prick, testing procedure, timing of results)

The meaning of an HIV-positive and an HIV-negative result

The potential for incorrect results if a person already on ART is given an HIV test

Information regarding the follow-up services that are available in the case of an HIV-positive test result

Assess personal risky behaviour and discuss risk reduction plan

Information about support mechanisms, who will the patient tell about the results? Where can he get support?

Individual testing procedure

Ask for consent for testing

Address any fears related to testing

Post-test individual HIV counselling check list

For NEGATIVE results

Ask the patient if he is ready to receive the results

Give the results simply and clear

Explain the meaning of negative HIV test and the window period and assess if there has been at risk behaviour in the preceding 3 months; recommend re-testing in case of recent exposure

Discuss the importance of remaining negative by educating on methods of prevention (provision of male and female condoms and explain how to use them)

Emphasize on the importance of knowing the HIV status of sexual partner(s) and give information about the availability of partner and couples testing services

Patient education and counselling at screening of TB

For POSITVE results

Ask the patient if he is ready to receive the results

Give the results simply and clear

Check with open-ended questions that the person understand the meaning of the result

Allow and encourage the patient to ask questions

Let the patient talk about his feelings about the results

Acknowledge the shock of the diagnosis ; offer support

Determine how the patient will get through the next few hours

Discuss eventual disclosure of the results and to whom

Discuss how to protect partner(s) from infection and explain use of condoms

Encourage and offer HIV testing for sexual partners, children and other family members of the client

Provide clear information on ART and its benefits for maintaining health and reducing the risk of HIV transmission, as well as where and how to obtain ART

Encourage and provide time for the client to ask additional questions

Topics

Give emotional support regarding the diagnosis

Assess previous knowledge and explain facts on TB disease

- What is TB (Card 1)
- What are the signs and symptoms of active TB (Card 2)
- What are the ways of transmission and prevention of TB (Card 3)
- What is the relationship between HIV and TB (Card 14)
- What is the difference between drug-sensitive and drug-resistant TB

Assess previous knowledge and explain the facts on TB treatment:

- What does the treatment consist of (Card 5)
- How to adhere (Card 15)
- Side effects of treatment (Card 6)
- Clinic follow-up for DSTB patients
- Clinic follow-up for DSTB patients

Explain risk for family members and ask the patient to bring any family member with TB symptoms and all children < 5 years old

Make a plan on how to adhere to TB treatment (getting ready to start treatment, support system, getting to the clinic, medication schedule, managing missed doses, reminder strategies, storing medication)

When	Patients suspected to have active TB disease, including DR-TB, referred for sputum collection
Mode	In group or individually
Duration	15 minutes

Topics

Explain basic facts on TB (what is TB, signs & symptoms, transmission, prevention, relationship with HIV) (Card 1-2-3)

Explain the procedure of TB diagnosis

Explain how to produce sputum (Card 4)

Patient education and counselling at the start of DSTB treatment

When	Before or at the day of TB treatment initiation
Mode	Individual
Duration	30-45 min

Patient education and counselling after starting DSTB treatment

When	One week after treatment initiation or at the first visit after commencing treatment
Mode	Individual
Duration	30 min

Topics

Give emotional support

Evaluate adherence to TB medication (annex 8) and work around any difficulties taking medication since starting

Review knowledge on TB disease and its treatment

Explain monitoring tests for TB treatment

Explain on use of traditional medication, alcohol and drugs in combination with TB treatment

Remind patient to bring any family member with TB symptoms and all children < 5 years old (if the patient didn't yet)

Patient education and counselling at the end of DSTB intensive phase

When At the end of DSTB intensive phase

Mode Individual or in group

Duration 15 min

Topics

Evaluate adherence

Solve any adherence issues

Explain the change in drug regimen for the continuation phase

Explain the need to continue to take treatment throughout the maintenance phase, even if the patient might feel better. Assess and reinforce the patient's motivation to continue treatment

Remind patient to bring any family member with TB symptoms and all children < 5 years old (if the patient didn't yet)

Additional PEC sessions throughout DSTB treatment

When At any moment of TB treatment if adherence problems are detected

Mode Individual

Duration 20 min

Topics

Evaluate adherence

Solve any adherence issues

Explain the need to continue to take treatment throughout the treatment, even if the patient might feel better. Assess and reinforce the patient's motivation to continue treatment

Remind patient to bring any family member with TB symptoms and all children < 5 years old (if the patient didn't yet)

Support group TB sessions

When At any moment of TB treatment if adherence problems are detected

Mode	Group
Duration	45 minutes
Methodology	Discuss challenges and share personal experience without being blamed, judged or stigmatised
	Can be facilitated by staff member or not
	Attention to infection control concerns

Appendix 15: Anti-TB dosages for children⁶

Intensive phase

Weight (kg)	Paediatric formulations		Adult formulations		
	HZ _R 50/150/75	E 100	E 400	H 100	EHZ _R 275/75/400/150
4	1 tab	1 tab			
5	1 tab	1 tab			
6	1 tab	1 tab			
7	1 tab	1 tab			
8	2 tab	2 tab			
9	2 tab	2 tab			
10	2 tab	2 tab			
11	2 tab	2 tab			
12	3 tab	3 tab			
13	3 tab	3 tab			
14	3 tab	3 tab			
15	3 tab	3 tab			
16	4 tab	–	1 tab		
17	4 tab	–	1 tab		
18	4 tab	–	1 tab		
19	4 tab	–	1 tab		
20	4 tab	–	1 tab		
21	4 tab	–	1 tab		
22	4 tab	–	1 tab		
23	–	–	–	1 tab	2 tab
24	–	–	–	1 tab	2 tab
25	–	–	–	1 tab	2 tab
26	–	–	–	1 tab	2 tab
27	–	–	–	1 tab	2 tab
28	–	–	–	1 tab	2 tab
29	–	–	–	1 tab	2 tab
30-34	–	–	–	–	2 tab
35-39	–	–	–	–	2 ½ tab
40-54	–	–	–	–	3 tab
55-70	–	–	–	–	4 tab
> 70	–	–	–	–	5 tab

⁶ Based on the Appendix 8a of MSF TB Guideline 2014

Continuation phase

Weight (kg)	Paediatric formulation		Adult formulation
	HR 50/75	HR 75/150	
4	1 tab		
5	1 tab		
6	1 tab		
7	1 tab		
8	2 tab		
9	2 tab		
10	2 tab		
11	2 tab		
12	3 tab		
13	3 tab		
14	3 tab		
15	–	2 tab	
16	–	2 tab	
17	–	2 tab	
18	–	2 tab	
19	–	2 tab	
20	–	2 tab	
21	–	2 tab	
22	–	3 tab	
23	–	3 tab	
24	–	3 tab	
25	–	3 tab	
26	–	3 tab	
27	–	3 tab	
28	–	3 tab	
29	–	3 tab	
30-34	–	2 tab	
35-39	–	2 ½ tab	
40-54	–	3 tab	
55-70	–	4 tab	
> 70	–	5 tab	
	Daily dosing in patients < 30 kg		Daily dosing in patients ≥ 30 kg
E	15 to 25 mg/kg once daily	15 to 25 mg/kg once daily	
H	7 to 15 mg/kg once daily	4 to 6 mg/kg once daily	
Z	30 to 40 mg/kg once daily	20 to 30 mg/kg once daily	
R	10 to 20 mg/kg once daily	8 to 12 mg/kg once daily	

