TB LAM in urine will be tested in all Malakal patients (starting from November 2021) and the result (negative/positive and grade 1-4) recorded in the CRF Lab form. The result will be shared with Research Manager who will only communicate to clinicians in case of HIV-infected patient; in these patients, TB LAM will be used as per clinical protocol.

3. Sample handling and storage

Respiratory specimens will be collected at the clinic and samples will be kept between 2 and 8°C until processed. Processing will be done within the 24 hours and not more than 72 hours after collection. A sterile stool container and instructions will be provided to the parent or guardian for specimen collection and handling. Following delivery to the laboratory, the stool specimen will be kept in a cool dry place and processed within 2 hours. Samples obtained in this study will adhere to all local laboratory procedures governing the storage of biological specimens.

c. Linkage to care for HIV/TB patients

All patients HIV positive will be enrolled into **HIV care** either in MSF program (Malakal) or MoH programs (Bissau). MSF will guarantee that all children will be started on ART after 2 weeks of TB treatment (or as soon as possible if TB has been excluded) or differed to 4-6 weeks in case of TB meningitis.

All TB cases (confirmed or unconfirmed) will be enrolled in **TB care** in MSF program (Malakal) or MoH program (Bissau). MSF will ensure all patients to be started on adequate weight-based dose fix combinations and followed up during the length of treatment. All children diagnosed of DRTB will be initiated on DRTB treatment regimen according to national recommendation.

In patients where stool samples yield positive results and sputum tests are negative, stool results will be communicated to Study Coordinator on site for interpretation and appropriate clinical management. Where stools results are concordant with sputum results, no additional information will be provided.

As a transversal study, it is not foreseen to follow-up patients for study purposes. The follow-up will be required though for the study “Evaluating POCUS to improve TB diagnosis in children”.

d. Data collection

The following information will be noted in an individual case study report form (CRF) for each participant:

1. DEMOGRAPHIC INFORMATION AND INFORMED CONSENT OF PATIENTS:

- Study code
- Date of birth / age
- Sex
- Parent or guardian's informed consent: Yes / No

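### At eight weights under 30 kg, the Appendix 15 tablet counts give doses outside the mg/kg ranges printed beneath them, chiefly intensive-phase Z at 6 and 7 kg

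*Combined protocol and SAP*

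**What the plan says.** Appendix 15 has two tablet tables, one for the intensive phase and one for the continuation phase. Each has one row per kilogram from 4 to 29 kg and wider bands from 30 kg upward. Beneath them it prints daily ranges per drug. Under "Daily dosing in patients < 30 kg" these are:

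- Z: "30 to 40 mg/kg once daily"
- E: "15 to 25 mg/kg once daily"
- R: "10 to 20 mg/kg once daily"
- H: "7 to 15 mg/kg once daily"

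From 30 kg the Z range changes to "20 to 30 mg/kg once daily", H to 4-6 mg/kg and R to 8-12 mg/kg, while E stays the same. A footnote says that the appendix is based on an MSF TB guideline of 2014.

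The appendix gives no rounding tolerance and no rule of precedence between the tablet counts and the ranges.

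Section 8.c (Linkage to care) makes the general commitment: "MSF will ensure all patients to be started on adequate weight-based dose fix combinations". It does not cite Appendix 15.

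**The concern.** A weight-banded tablet table and a mg/kg range on the same page are two statements of the same dose. A clinician who checks one against the other should get the same answer, or be told how much difference to accept. At some weights neither is so.

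The largest gaps are at 6 and 7 kg. Those weights are plausible here, because Section 7.d admits children from 6 months of age and Section 8.a names severely malnourished children as a population of interest. At stake is the clarity of the dosing reference for low-weight children. Treatment is not an endpoint, so sensitivity, specificity and the sample size do not depend on it.

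**Working it through.** **Inputs, all from Appendix 15.** Strengths are read in label order.

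- Paediatric intensive tablet: H 50, Z 150, R 75 mg. Separate ethambutol tablets: E 100 and E 400 mg. Supplementary isoniazid tablet: H 100 mg.
- Adult intensive tablet, printed as "EHZ _R 275/75/400/150": E 275, H 75, Z 400, R 150 mg.
- Continuation tablets: HR 50/75 and HR 75/150 mg.

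The order is supported within the appendix: the H and R strengths of the two continuation tablets equal those of the two combination tablets.

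**Formula.** Dose (mg/kg/day) = tablets × mg per tablet ÷ weight in kg. Each row is evaluated at its printed whole-kilogram weight. A value exactly on a limit counts as inside.

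**Rows that reproduce the printed range.** Z is 150/5 = 300/10 = 450/15 = 600/20 = 30.0, exactly on the floor. At 4, 8, 12 and 16 kg it is 37.5. The tablet reading therefore fits the ranges at most weights.

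**Rows that do not:**

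| Phase, drug | Weight (kg) | Calculation | mg/kg | Printed limit | Gap |
|---|---|---|---|---|---|
| Intensive Z | 6 | 1 × 150 / 6 | 25.0 | 30 (floor) | 17% below |
| Intensive Z | 7 | 1 × 150 / 7 | 21.4 | 30 | 29% below |
| Intensive Z | 11 | 2 × 150 / 11 | 27.3 | 30 | 9% below |
| Intensive Z | 21 | 4 × 150 / 21 | 28.6 | 30 | 4.8% below |
| Intensive Z | 22 | 4 × 150 / 22 | 27.3 | 30 | 9% below |
| Intensive Z | 27 | 2 × 400 / 27 | 29.6 | 30 | 1.2% below |
| Intensive Z | 28 | 2 × 400 / 28 | 28.6 | 30 | 4.8% below |
| Intensive Z | 29 | 2 × 400 / 29 | 27.6 | 30 | 8% below |
| Intensive E | 7 | 1 × 100 / 7 | 14.3 | 15 (floor) | 4.8% below |
| Continuation R | 22 | 3 × 150 / 22 | 20.5 | 20 (ceiling) | 2.3% above |

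Gap = |dose − limit| ÷ limit; for example (30 − 21.4)/30 = 0.29.

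**Counts under 30 kg.** In the intensive phase, 26 rows × 4 drugs = 104 cells, of which 9 are outside, in 8 rows. In the continuation phase, 26 × 2 = 52 cells, of which 1 is outside. Together that is 10 of 156. H is inside everywhere, and R is inside throughout the intensive phase.

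**From 30 to 70 kg.** Every drug is inside at both ends of every band in both phases. For Z:

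- 30-34 kg: 800/30 = 26.7 to 800/34 = 23.5
- 35-39 kg: 1000/35 = 28.6 to 1000/39 = 25.6
- 40-54 kg: 1200/40 = 30.0 to 1200/54 = 22.2
- 55-70 kg: 1600/55 = 29.1 to 1600/70 = 22.9

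**Could text extraction explain it?** The Z results use only the first tablet column up to 22 kg and the last column at 27-29 kg, so they do not depend on how the E columns align. The half-tablet entry at 35-39 kg survived extraction, which makes a lost half tablet elsewhere unlikely. The E and R results do depend on the column reading.

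**The case against.** The strongest reply is that fixed-dose tablets in whole-kilogram rows cannot hit every range. H, Z and R share one tablet, so none of them can be adjusted alone, and the mg/kg lines may be reference values behind a practical table. This stands for the gaps under 5%: Z at 21, 27 and 28 kg, E at 7 kg and R at 22 kg all fit ordinary rounding. It is weaker for Z at 11, 22 and 29 kg, and it does not readily cover 17% and 29% at 6 and 7 kg. The appendix states no tolerance, and its use of a half tablet at 35-39 kg means that a whole-tablet rule cannot be assumed.

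A reader might also infer four stronger things, none of which the documents support:

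- **That a child dosed from the table is generally outside the limits.** Most rows, and all bands from 30 to 70 kg, are inside.
- **That the table and the ranges cannot both be right.** The appendix does not say that the ranges are hard limits, and the source guideline is not available to show whether the mismatch arose in copying or was already there.
- **That every TB case in the study is dosed from this page.** Section 8.c does not cite it and sends drug-resistant cases to national recommendations. Section 11.d makes the national programme responsible for starting and following treatment in Bissau, the site of 184 of the 327 planned children. Section 16 lists Appendix 15 without the asterisk that marks study-specific appendices.
- **That patient safety is shown to be affected.** The documents support only that it could be, for children who are treated from this page.

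**Conclusion.** The point holds as a narrow internal inconsistency. All ten discrepant cells fall within eight weights: 6, 7, 11, 21, 22, 27, 28 and 29 kg in the intensive phase, with the continuation-phase cell at 22 kg. Only Z at 6 and 7 kg is more than 10% from its limit. The defect is the disagreement together with the absence of any stated tolerance or precedence. Which figure is right cannot be settled from the documents, and no dose is proposed here.

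The conclusion assumes that strengths are read in label order, that tablet columns stand as extracted, and that each row applies at its printed weight. It is worth correcting because the largest gaps sit at weights that this study can be expected to enrol. It has no bearing on the objectives, endpoints, sample size or analysis.

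**What to change.** The sponsor should check both the tablet table and the mg/kg ranges against the source guideline and reconcile them at the eight intensive-phase weights and at 22 kg in the continuation phase. The appendix should then state which of the two governs and what tolerance, if any, is accepted. The choice belongs to the sponsor's clinical team.

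The cost is one corrected appendix page. Section 16 says that many appendices are shared with the companion ultrasound (POCUS) study, so if this page is among them the same correction should be made there.

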Appendix 16a: Weight for height in children from 5 to 10 year old

RECONSTRUCTED FROM BMI charts: height between 120,5 and 140,0 cm									
Reconstruction based on WHO 2007 references									
Older children from 60 months to 10 years (110,0 - 140,0 cm)									
MALE		Weight-for-Height (Standing up)					FEMALE		
-3	-2	-1	Median	cm	Median	-1	-2	-3	
14.4	15.6	17.0	18.5	110	18.6	17.0	15.5	14.2	
14.5	15.8	17.1	18.7	110.5	18.8	17.1	15.7	14.4	
14.6	15.9	17.3	18.9	111	19.0	17.3	15.8	14.5	
14.8	16.0	17.5	19.1	111.5	19.2	17.5	16.0	14.7	
14.9	16.2	17.6	19.2	112	19.4	17.7	16.2	14.8	
15.0	16.3	17.8	19.4	112.5	19.6	17.9	16.3	15.0	
15.2	16.5	18.0	19.6	113	19.8	18.0	16.5	15.1	
15.3	16.6	18.1	19.8	113.5	20.0	18.2	16.7	15.3	
15.4	16.8	18.3	20.0	114	20.2	18.4	16.8	15.4	
15.6	16.9	18.5	20.2	114.5	20.5	18.6	17.0	15.6	
15.7	17.1	18.6	20.4	115	20.7	18.8	17.2	15.7	
15.8	17.2	18.8	20.6	115.5	20.9	19.0	17.3	15.9	
16.0	17.4	19.0	20.8	116	21.1	19.2	17.5	16.0	
16.1	17.5	19.2	21.0	116.5	21.3	19.4	17.7	16.2	
16.2	17.7	19.3	21.2	117	21.5	19.6	17.8	16.3	
16.4	17.9	19.5	21.4	117.5	21.7	19.8	18.0	16.5	
16.5	18.0	19.7	21.6	118	22.0	19.9	18.2	16.6	
16.7	18.2	19.9	21.8	118.5	22.2	20.1	18.4	16.8	
AGE	16.8	18.3	20.0	22.0	119	22.4	20.3	18.5	16.9
year:month	16.9	18.5	20.2	22.2	119.5	22.6	20.5	18.7	17.1
06:08	17.1	18.6	20.4	22.4	120	22.8	20.7	18.7	17.2
06:09	17.5	19.0	20.6	22.4	120.5	22.8	20.8	18.8	17.3
06:10	17.9	19.2	20.8	22.5	121	22.9	20.9	18.9	17.3
6:11 / 7:00	18.0	19.3	21.0	22.9	121.5	23.0	20.9	19.0	17.4
07:01	18.3	19.6	21.1	23.1	122	23.1	21.0	19.1	17.6
07:02	18.5	19.8	21.3	23.3	122.5	23.3	21.1	19.2	17.7
07:03	18.6	20.0	21.6	23.4	123	23.4	21.2	19.4	17.9
07:04	18.8	20.1	21.8	23.8	123.5	23.6	21.4	19.5	18.0
07:05	18.9	20.3	22.0	24.0	124	23.8	21.5	19.7	18.1
07:06	19.1	20.5	22.2	24.2	124.5	24.2	21.7	19.8	18.3
07:07	19.2	20.6	22.3	24.4	125	24.4	22.0	20.0	18.4
07:08	19.4	20.8	22.5	24.6	125.5	24.6	22.2	20.3	18.7
07:09	19.7	21.1	22.7	24.9	126	24.9	22.4	20.5	18.9
07:10	19.8	21.3	23.0	25.1	126.5	25.1	22.6	20.6	19.0
7:11 / 8:00	20.0	21.5	23.2	25.3	127	25.3	22.7	20.8	19.2
08:01	20.2	21.6	23.4	25.7	127.5	25.5	23.1	21.0	19.3
08:02	20.3	21.8	23.6	25.9	128	25.9	23.3	21.1	19.5
08:03	20.5	22.0	23.8	26.1	128.5	26.1	23.4	21.5	19.6
08:04	20.6	22.3	24.1	26.3	129	26.3	23.6	21.6	20.0
08:05	21.0	22.5	24.3	26.7	129.5	26.7	24.0	21.8	20.1
08:06	21.1	22.6	24.5	26.9	130	26.9	24.2	22.0	20.3
08:07	21.3	22.8	24.7	27.1	130.5	27.1	24.4	22.1	20.4
08:08	21.5	23.0	24.9	27.3	131	27.5	24.5	22.5	20.6
08:09	21.6	23.2	25.2	27.7	131.5	27.7	24.9	22.7	20.9
8:10 / 8:11	21.8	23.5	25.4	27.9	132	28.1	25.1	22.8	21.1
09:00	22.1	23.7	25.6	28.1	132.5	28.3	25.3	23.0	21.2
09:01	22.3	23.9	25.8	28.5	133	28.5	25.6	23.3	21.4
09:02	22.5	24.1	26.2	28.7	133.5	28.9	25.8	23.5	21.6
09:03	22.6	24.2	26.4	28.9	134	29.1	26.0	23.7	21.9
9:04 / 9:05	22.8	24.6	26.6	29.3	134.5	29.5	26.4	23.9	22.1
09:06	23.1	24.8	27.0	29.5	135	29.7	26.6	24.2	22.2
09:07	23.3	25.0	27.2	29.9	135.5	29.9	26.8	24.4	22.4
09:08	23.5	25.2	27.4	30.1	136	30.3	27.2	24.6	22.8
09:09	23.7	25.5	27.6	30.4	136.5	30.6	27.4	25.0	22.9
09:10	23.8	25.7	28.0	30.8	137	31.0	27.6	25.2	23.1
9:11 / 10:00	24.2	25.9	28.2	31.0	137.5	31.2	28.0	25.3	23.3
10:01	24.4	26.3	28.6	31.4	138	31.6	28.2	25.5	23.6
10:02	24.6	26.5	28.8	31.7	138.5	31.8	28.4	25.9	23.8
10:03	24.7	26.7	29.0	32.1	139	32.3	28.8	26.1	24.0
10:04	25.1	26.9	29.2	32.3	139.5	32.5	29.0	26.3	24.1
10:05	25.3	27.2	29.6	32.5	140	32.9	29.4	26.7	24.5

Appendix 16b: Weight for height in adolescents

Weight adaptations between 140,0 (BMI charts WHO 2007) to 145,0 cm (NCHS 198

Reconstruction based on NCHS-CDC-WHO 1982 references

Adolescents from 10 to approx 18 years (140,0 - 165,0 cm)

MALE		Weight-for-Height (Standing up)					FEMALE		
70%	80%	85%	Median	cm	Median	85%	80%	70%	
25.1	27.2	29.6	32.5	140	32.9	29.4	26.7	24.5	
25.2	27.4	29.7	33.0	140.5	33.2	29.6	26.8	24.7	
25.2	27.6	29.9	33.4	141	33.6	29.8	27.0	24.9	
25.3	28.0	30.0	33.8	141.5	33.8	30.2	27.4	25.0	
25.4	28.2	30.2	34.1	142	34.1	30.4	27.6	25.2	
25.4	28.4	30.3	34.7	142.5	34.8	30.7	27.8	25.6	
25.5	28.8	30.5	35.0	143	35.6	31.1	28.0	25.7	
25.6	29.0	30.6	35.3	143.5	36.0	31.3	28.4	25.8	
25.6	29.1	30.8	35.7	144	36.4	31.4	28.6	25.9	
25.7	29.2	30.9	36.1	144.5	36.9	31.5	29.1	26.0	
25.8	29.2	31.0	36.5	145	37.1	31.5	29.7	26.0	
25.8	29.5	31.3	36.8	145.5	37.4	31.8	29.9	26.2	
26.0	29.7	31.6	37.2	146	37.8	32.1	30.2	26.5	
26.3	30.0	31.9	37.6	146.5	38.1	32.4	30.5	26.7	
26.5	30.3	32.2	37.9	147	38.4	32.6	30.7	26.9	
26.8	30.6	32.5	38.3	147.5	38.8	33.0	31.0	27.2	
27.0	30.9	32.8	38.6	148	39.1	33.2	31.3	27.4	
27.3	31.2	33.1	39.0	148.5	39.5	33.6	31.6	27.7	
27.5	31.5	33.4	39.3	149	39.8	33.8	31.8	27.9	
27.8	31.7	33.7	39.7	149.5	40.1	34.1	32.1	28.1	
28.0	32.0	34.0	40.0	150	40.5	34.4	32.4	28.4	
28.3	32.3	34.3	40.4	150.5	40.8	34.7	32.6	28.6	
28.5	32.6	34.7	40.8	151	41.2	35.0	33.0	28.8	
28.8	32.9	34.9	41.1	151.5	41.5	35.3	33.2	29.1	
29.1	33.2	35.3	41.5	152	41.9	35.6	33.5	29.3	
29.3	33.5	35.6	41.9	152.5	42.3	36.0	33.8	29.6	
29.6	33.8	35.9	42.3	153	42.6	36.2	34.1	29.8	
29.8	34.1	36.2	42.6	153.5	43.0	36.6	34.4	30.1	
30.1	34.4	36.6	43.0	154	43.4	36.9	34.7	30.4	
30.4	34.7	36.9	43.4	154.5	43.8	37.2	35.0	30.7	
30.7	35.0	37.2	43.8	155	44.2	37.6	35.4	30.9	
30.9	35.4	37.6	44.2	155.5	44.6	37.9	35.7	31.2	
31.2	35.7	37.9	44.6	156	45.1	38.3	36.1	31.6	
31.5	36.0	38.3	45.0	156.5	45.5	38.7	36.4	31.9	
31.8	36.3	38.6	45.4	157	46.0	39.1	36.8	32.2	
32.1	36.7	38.9	45.8	157.5	46.5	39.5	37.2	32.6	
32.4	37.0	39.3	46.2	158	47.0	40.0	37.6	32.9	
32.7	37.3	39.6	46.6	158.5	47.6	40.5	38.1	33.3	
33.0	37.7	40.0	47.1	159	48.2	41.0	38.6	33.7	
33.3	38.0	40.4	47.5	159.5	48.9	41.6	39.1	34.2	
33.6	38.4	40.8	48.0	160	49.7	42.2	39.8	34.8	
33.9	38.7	41.1	48.4	160.5	50.5	42.9	40.4	35.4	
34.2	39.1	41.5	48.8	161	51.6	43.9	41.3	36.1	
34.5	39.4	41.9	49.3	161.5	52.8	44.9	42.2	37.0	
34.8	39.8	42.3	49.8	162	54.5	46.3	43.6	37.8	
35.1	40.2	42.7	50.2	162.5	56.1	47.7	44.9	38.3	
35.5	40.5	43.1	50.7	163	56.4	47.9	45.1	38.8	
35.8	40.9	43.5	51.1	163.5	56.7	48.2	45.4	39.0	
36.1	41.3	43.9	51.6	164	57.0	48.4	45.6	39.5	
36.5	41.7	44.3	52.1	164.5	57.3	48.7	45.8	39.8	
36.8	42.1	44.7	52.6	165	57.6	48.9	46.0	40.0	

Appendix 17: CRF Lab

Patient study code:

Respiratory Xpert MTB/RIF Ultra

Date of sample collection: / /

Type of procedure:

- Spontaneous sputum
- Naso-pharyngeal aspirate
- Gastric aspiration

Date of Xpert MTB/RIF performed: / /

Result of Xpert MTB/RIF:

- Negative
- Positive RIF resistance negative
- Positive RIF resistance positive
- Indeterminate

Respiratory Xpert MTB/RIF Ultra (second sample if done)

Date of respiratory sample collection: / /

Type of procedure:

- Spontaneous sputum
- Naso-pharyngeal aspirate
- Gastric aspiration

Date of Xpert MTB/RIF in respiratory sample performed: / /

Result of Xpert MTB/RIF:

- Negative
- Positive RIF resistance negative
- Positive RIF resistance positive
- Indeterminate

Validated extra pulmonary Xpert MTB/RIF Ultra

Date of sample collection: / /

Type of sample:

- Lymph node
- Pus or tissue Specify location:
- Pleural effusion
- CSF
- Ascetic fluid
- Other Specify:

Date of Xpert MTB/RIF in respiratory sample performed: / /

Result of Xpert MTB/RIF:

- Negative
- Positive RIF resistance negative
- Positive RIF resistance positive
- Indeterminate

Validated extra pulmonary Xpert MTB/RIF Ultra

Date of sample collection: / /

Type of sample:

- Lymph node
- Pus or tissue Specify location:

Pleural effusion

CSF

Ascetic fluid

Other

Specify:

Date of Xpert MTB/RIF in respiratory sample performed: / /

Result of Xpert MTB/RIF:

Negative

Positive RIF resistance negative

Positive RIF resistance positive

Indeterminate

Stools Xpert MTB/RIF Ultra

Date of stools collection: / /

Date of Xpert MTB/RIF in stools performed: / /

Result of Xpert MTB/RIF:

Negative

Positive RIF resistance negative

Positive RIF resistance positive

Indeterminate

Stools Xpert MTB/RIF Ultra (second sample if done)

Date of stools collection: / /

Date of Xpert MTB/RIF in stools performed: / /

Result of Xpert MTB/RIF:

Negative

Positive RIF resistance negative

Positive RIF resistance positive

Indeterminate

Urine Xpert MTB/RIF Ultra

Date of urine collection: / /

Date of Xpert MTB/RIF in urine performed:

Result of Xpert MTB/RIF:

Negative

Positive RIF resistance negative

Positive RIF resistance positive

Indeterminate

Urine Xpert MTB/RIF Ultra (second sample if done)

Date of urine collection: / /

Date of Xpert MTB/RIF in urine performed: / /

Result of Xpert MTB/RIF:

Negative

Positive RIF resistance negative

Positive RIF resistance positive

Indeterminate

